4.5 Special Consent/Populations

A. Minors-Subjects Who Are Not Yet Adults

- **Parental Permission**

Parents will provide permission for participation of their children.

- **Non-Parental Permission**

Not applicable.

- **Assent Process**

Based on children's chronological age for this study (6 to 12 months old) assent is not developmentally appropriate. However, study staff will ensure children's comfort when participating in assessments.

- **Documentation of Assent**

- Not applicable
- **Reaching Age of Majority During Study**
- Not applicable

B. Wards of the State

- Not applicable
- **Research Outside of NJ Involving Minors**
- Not applicable

C. Non-English-Speaking Subjects

- Participants who speak English or Spanish will be included in this study
- **Process for Non-English-Speaking Subjects**
- Participants who identify Spanish as their preferred language will be recruited. Research assistants speak Spanish fluently and will use translated informed consent documents.
- **Short Form Consent for Non-English Speakers**
- Not applicable

D. Adults Unable to Consent / Cognitively Impaired Adults (for interventional studies)

- Not applicable
- **NJ Law-Assessment of Regaining the Capacity to Consent**
- Not applicable.
- **Capacity to Consent**
- Not applicable.
- a. **NJ Law-Selecting A Witness**
- Not applicable
- b. **Removing a Subject**
- Not applicable.

4.6 Economic Burden and/or Compensation for Subjects

A. Expenses

No additional expenses for participants are anticipated. However, for those receiving text messages, standard message rates apply with receiving and or sending text messages if participants do not have an unlimited text message plan.

B. Compensation/Incentives

Parent participants will be compensated for their time. Participants will receive a \$50 retail gift card at the initial visit and an additional \$50 gift card after completing 2 follow up visits occurring at 9 months and 18 months (Total=\$150). Participants will be texted/mailed links to electronic gift cards and/or given the plastic gift card in person.

Clinicians and ROR experts will not be compensated for their time.

C. Compensation Documentation

Participant compensation will be managed using an Excel spreadsheet. A study team member will document the study ID and gift card number which will be reviewed by the PI.

4.7 Risks of Harm/Potential for Benefits to Subjects

A. Description of Risks of Harm to Subjects

- **Reasonably Foreseeable Risks of Harm**

The potential risks to the participants will be minimal. All study personnel will receive appropriate training in human subjects research and patient confidentiality. During assessments there will be the potential for psychological discomfort due to the personal nature of questions asked and for the potential loss of confidentiality. This risk is minimized

by conducting assessments and interviews in private settings. We have an NIH Certificate of Confidentiality, which will be issued automatically, and we have included this language in our consent forms. Participants will be reminded that participation is completely voluntary and they may withdraw from the study at any time.

▪ **Risk of Harm from an Intervention on a Subject with an Existing Condition**

Not applicable.

▪ **Other Foreseeable Risks of Harm**

There is a minor risk of loss of confidentiality. This risk is minimized by measures taken by the PI and the study team to ensure confidentiality. Risks are reduced by using secure files; storing master list files on secure, password-protected research servers and computers; and storing data files on REDCap, a secure, web-based application used for human subjects research studies. Whenever possible data will be directly entered into REDCap to minimize the risk of breach of confidentiality.

▪ **Observation and Sensitive Information**

For qualitative data field notes will not include identifiable data. Video recordings of parent-child interactions will be deleted once coded.

B. Procedures which Risk Harm to Embryo, Fetus, and/or Pregnant Subjects

Not applicable.

C. Risks of Harm to Non-Subjects

Not applicable.

D. Assessment of Social Behavior Considerations

Not applicable

E. Minimizing Risks of Harm

The study team will employ several measures to minimize potential risks. Only trained study team members supervised by the PI will have contact with participants and access to the study data. It is possible that participants may feel uncomfortable during assessments. Participants will be reminded that they may discontinue participation at any time. There is also a small risk of breach of confidentiality. Participants will receive a unique code number and names will not appear on data. The key list linking participant identification with numeric codes will be locked in a secure filing cabinet and the key will be destroyed when data analysis is complete. All data will be stored on password protected computers or REDCap a secure server. When possible, information will be directly entered into REDCap.

▪ **Certificate of Confidentiality**

- We have an NIH Certificate of Confidentiality, which will be issued automatically, and we have included this language in our consent forms.
- The NIH Certificate of Confidentiality does not supersede reporting that federal, state, or local laws require, such as laws that require reporting of child abuse. Participants will be advised during the consent process for audio- and/or video-recording that there are instances where a breach of confidentiality is required by law. These are instances where suspected harm is occurring to a child or other vulnerable person.

▪ **Provisions to Protect the Privacy Interests of Subjects**

Only trained study team members will perform study procedures. Participation is completely voluntary and participants can discontinue their participation at any time.

F. Potential Benefits to Subjects

All participants will receive the standard Reach Out and Read intervention an evidence-based intervention and a pediatric care standard. Although not guaranteed participants may receive additional benefits from the other study arms.

5.0 Special Considerations

5.1 Health Insurance Portability and Accountability Act (HIPAA)

The following identifying information will be collected to facilitate recruitment and retention: child name, child date of birth, parent name, parent phone number, parent email address, family mailing

address. Identifying information will be stored separately from study data in a secure research drive or REDCap using a study ID number.

5.2 Family Educational Rights and Privacy Act (FERPA)

Not applicable

5.3 NJ Access to Medical Research Act (Surrogate Consent)

Not applicable

5.4 General Data Protection Regulation (GDPR)

Not applicable

5.5 Code of Federal Regulations Title 45 Part 46 (Vulnerable Populations)

A. Special Populations

Given that early childhood experiences are critical for school readiness and the importance of parent behaviors including shared reading for development and behavior beginning in infancy, this proposal includes both children and their parents as subjects. No greater than minimal risk to participating children is presented in this study. Children will only participate with the permission of their parent or guardian as outlined above. Given that all children will be age 6 to 12 months of age at enrollment assent is not developmentally appropriate.

6.0 Data Management Plan

6.1 Data Analysis

1. Enrollment: We will recruit 630 parent-child dyads (210 per arm) over a 24-month time period. We expect that 80% of the 630 enrolled parent-child dyads will complete the study, leaving 525 parent-child dyads (175 in each arm).

2. Sample size and power:

630 parent-child dyads (210 per arm) will be sufficient to achieve 80% power to detect a 0.3 standard deviation (SD) difference in the primary endpoints language scores on the EOWPVT-4 and social-emotional skill scores on the DECA at 18 months between (1) ROR + texts and ROR only and (2) ROR + texts + Central Intake and ROR + texts, assuming approximately 20% attrition based on our past work²⁹ and using 0.05 significance level. An effect size of 0.3 SD difference would be clinically meaningful since it would be associated with a detectable difference in later cognitive functioning, based on work from a prospective cohort.³⁰ The proposed sample size will provide 99.9% power to detect a 0.6 SD difference between the community resource arm and ROR only, based on the expected additive effects of the text message and enhanced access to poverty-reducing resources.

3. Analysis:

Distributions of baseline characteristics will be summarized overall as well as by randomization group. We will assess the distribution of outcome data using descriptive statistics to check the assumption of normality for continuous variables. We will estimate mean outcomes for each treatment group as well as mean differences between groups (with confidence intervals). If any continuous outcomes are skewed, we attempt log-transformation or other to stabilize the variance and normalize distributions.

For aim 1, analysis will follow the intention to treat principle, in which participants are analyzed based on their group assignment, whether or not they receive the strategies for all outcomes. Because of the multiple, potentially highly correlated outcomes, the step-down minP method (a re-sampling approach), will be used to assess the effects of treatment³¹ across outcomes and timepoints within each domain (language development, social-emotional development, and parenting). We will use ANOVAs to evaluate treatment effects on adjusted outcomes. Specifically, for outcomes with more than one post-treatment timepoint and a baseline assessment, we will calculate individual- and baseline-adjusted outcomes from linear models with random individual-specific intercepts (random effect) and treatment and baseline as fixed effects. Then, the adjusted outcome is estimated as the observed outcome minus the best linear unbiased predictor (BLUP) of individual-specific intercept and baseline contribution. For outcomes with one post-treatment timepoint and a baseline assessment, a baseline-adjusted outcome

will be estimated from ANCOVA results as the observed outcome minus the estimated intercept and baseline contribution. The differences in means from ANOVAs focused on these adjusted outcomes will estimate treatment effects. For secondary outcomes, statistical significance will be set at $p < 0.05$ without adjustment for multiple comparisons. For language outcomes, we will adjust for child age and sex in sensitivity analyses.

For the mediation analyses in Aim 2, we will examine the extent to which the home literacy environment mediates the effect of the interventions on language skill and social-emotional skill acquisition using the product of coefficients method with each outcome at each post-intervention timepoint individually.³² We will calculate bootstrap bias-corrected confidence intervals ($n=5,000$) to estimate the proportion of treatment effect explained via the home literacy environment. While we expect the effect of the ROR + text messages (arm 2) intervention will mainly operate through the home literacy environment (parent investment) based on our conceptual framework, we expect that the ROR + text + Connecting NJ (arm 3) intervention will also have effects on parenting stress and other responsive parenting interactions (parental verbal responsiveness) through increased access to poverty-reducing community resources accounting for the greater hypothesized impact. We will test this more complex conceptual framework based on an adaptation of the Gershoff model using Structural Equation modeling without latent factors.

For aim 3, the mixed methods approach will allow us to systematically compare data on intervention implementation with the perspectives of parents and clinicians in an ongoing manner. Integration of quantitative and qualitative data will occur at the design, methods, and reporting levels. We will use a convergent design in which we collect quantitative data on key intervention components in the same time frame as we conduct observation (if possible) of study visits.

Parent-child observations will be analyzed by the study team, led by [name]. The observations will be coded according to parent-child interactive behaviors (did expected behaviors occur or not).

Practice and clinician surveys and clinician interviews will be analyzed using qualitative methods to identify changes and adaptations to ROR implementation protocols over time. The evaluation aims to determine what was implemented, how it was implemented, and what changes occurred to implementation over time. We also seek to understand how clinic context affected implementation. These qualitative findings will help inform our quantitative patient-reported outcomes.

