1.5 Sample Size Justification

We will recruit 630 Latino parent-child dyads (210 per arm) over a 24-month time period (Months 3-27). This sample size will be sufficient to achieve 80% power to detect a 0.3 standard deviation (SD) difference in language scores between (1) ROR + texts and ROR only and (2) ROR + texts + Connecting NJ and ROR + texts, assuming 20% attrition based on our ongoing work at one of the CHCs. An effect size of 0.3 SD difference would be clinically meaningful since it would be associated with a detectable difference in later cognitive functioning, based on work from a prospective cohort. The proposed sample size will provide 99.9% power to detect a 0.6 SD difference between the community resource arm and ROR only, based on the expected additive effects of the text message and enhanced access to poverty-reducing resources. We will plan for a conservative 24-month recruitment time period to account for seasonal variation in patient volumes and holidays to recruit the target sample (~2-3 participants /site/week).

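### 80% of 630 dyads is 504 completers (168 per arm), not 525 (175 per arm), and the 80% power at 0.3 SD belongs to the larger count

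*Combined protocol and SAP*

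**What the plan says.** Section 6.1, item 1, sets the enrolment target: "We will recruit 630 parent-child dyads (210 per arm) over a 24-month time period". The next sentence gives the expected yield: "We expect that 80% of the 630 enrolled parent-child dyads will complete the study, leaving 525 parent-child dyads (175 in each arm").

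Item 2 of the same section says this sample "will be sufficient to achieve 80% power to detect a 0.3 standard deviation (SD) difference in the primary endpoints language scores on the EOWPVT-4" and on the DECA at 18 months, for arm 2 against arm 1 and for arm 3 against arm 2. It does so "assuming approximately 20% attrition based on our past work" and "using 0.05 significance level". It adds: "The proposed sample size will provide 99.9% power to detect a 0.6 SD difference between the community resource arm and ROR only".

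Section 1.5 makes the same claim for language scores, with 630 dyads, 210 per arm, 80% power and 0.3 SD, "assuming 20% attrition based on our ongoing work at one of the CHCs". It gives no completer count. No section gives a retention rate that would turn 630 into 525.

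**The concern.** The sentence in item 1 contradicts itself. At 80% retention the trial ends with 504 dyads, and ending with 525 takes 83.3% retention. Because 525 is exactly 3 × 175, neither figure looks like a misprint.

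The contradiction carries into the power claim. The usual requirement for 80% power at 0.3 SD is about 175 per arm, which is the stated completer count. If attrition is the stated 20%, the trial does not reach that count, and the 80% power and the 20% attrition do not belong together.

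Expected completers and power are the planning figures against which retention is later judged, and section 6.3 has the DSMB review retention twice a year. If 525 were the yardstick, a trial that retained exactly 80% would look 21 dyads short.

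**Working it through.** **Inputs.** Enrolled: 630, 210 per arm (sections 1.5 and 6.1). Retention: 80% (6.1, item 1). Attrition: 20% (1.5), the same figure with a qualifier in 6.1, item 2. Difference: 0.3 SD, so SD = 1 on the standardised scale. Significance level: 0.05. Two assumptions are mine: the test is two-sided, and the comparison is between two arms without covariate adjustment.

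**Step 1: reproduce the plan's power.** Normal approximation, per arm:

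n = 2 × (1.960 + 0.842)² / 0.3² = 2 × 7.849 / 0.09 = 174.4, rounded up to 175.

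The t-test calculation gives 175.4. Power at 175 per arm is Φ(0.3 × √(175/2) − 1.960) = Φ(2.806 − 1.960) = Φ(0.846) = 80.1%, or 79.9% by noncentral t. The plan's 80% is therefore the power at 175 completers per arm. A one-sided 0.05 test would give 87.7% at 175 and 86.5% at 168, neither of which matches, so two-sided is the reading that fits.

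**Step 2: completers at the stated retention.**

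- 0.80 × 630 = 504, and 0.80 × 210 = 168 per arm.
- 525 − 504 = 21 dyads, or 7 per arm. The stated count is 21/504 = 4.2% too high.
- 525/630 = 83.3%, so 525 completers imply 16.7% attrition.

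**Step 3: a likely origin.** 175 × 1.2 = 210 and 525 × 1.2 = 630. To allow for 20% loss one divides by 0.8: 175/0.8 = 218.75, so 219 per arm and 657 in total. Starting from 175.4 gives 219.2, so 220 per arm and 660 in total. The numbers fit an inflation by 1.2 where division by 0.8 was needed. The documents do not say how the figure was obtained, so this is inference.

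**Step 4: what 168 per arm delivers.**

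Φ(0.3 × √(168/2) − 1.960) = Φ(2.750 − 1.960) = Φ(0.790) = 78.5%.

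| Completers per arm | Attrition from 210 | Power at 0.3 SD, normal | Power at 0.3 SD, t | Difference with 80% power (t) | Power at 0.6 SD (t) |
|---|---|---|---|---|---|
| 175 | 16.7% | 80.1% | 79.9% | 0.300 SD | 99.99% |
| 168 | 20.0% | 78.5% | 78.3% | 0.307 SD | 99.98% |

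The like-for-like loss at 0.3 SD is 1.6 points by either method. The claim of 99.9% power at 0.6 SD holds at both counts.

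**The case against.** **The effect is small.** The detectable difference of 0.307 SD rounds to the planned 0.3. The half-width of an unadjusted 95% interval moves from 1.96 × √(2/175) = 0.210 SD to 1.96 × √(2/168) = 0.214 SD. No test, analysis set or allocation rule in section 6.1 uses 525 or 175. All of this stands, and it limits the weight of the point.

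**The qualifier on attrition.** Item 2 says attrition is only roughly 20%, which might loosely cover 16.7%. That would defend the power sentence read alone. It does not repair item 1, which states 80% completion, or section 1.5, where 20% carries no qualifier.

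**Baseline adjustment.** Section 6.1 plans it where a baseline exists, and the DECA is measured at enrolment. A baseline correlation of 0.2 multiplies the variance by 1 − 0.2² = 0.96. Since 168/0.96 = 175, power returns to 80.1%. A shortfall is therefore not established for the DECA. The EOWPVT-4 is measured only at 18 months and has no baseline of its own, and the power statement does not invoke adjustment.

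**Intention to treat.** Analysing all 630 dyads would avoid the loss. But section 6.1 specifies no imputation, its power statement itself allows for attrition, and a child who misses the 18-month visit has no EOWPVT-4 score.

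The step-down minP adjustment, which the power statement does not mention, is a separate matter and adds nothing to this point.

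**Conclusion.** The plan is wrong as written. At 80% retention the expected number of completers is 504 (168 per arm), and the stated 525 (175 per arm) is 21 too many. The 80% power at 0.3 SD is the power at 175 completers per arm, which 210 enrolled per arm reach only if attrition is about 16.7%. At the stated 20%, power is 78.3% (t) or 78.5% (normal).

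The completer count needs only multiplication and rests on no assumption. The power figures assume a two-sided 0.05 test and an unadjusted two-arm comparison. They apply most directly to the EOWPVT-4; for the DECA, a modest baseline correlation would make up the difference. The design is not undermined: this is a planning figure to correct, and the power loss is under 2 points.

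**What to change.** Choose one of two corrections in section 6.1, items 1 and 2:

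- **Keep 20% attrition.** Change the expected completers to 504 (168 per arm), and state power as about 78% for 0.3 SD, or 80% for 0.31 SD.
- **Keep 525 completers.** Replace 80% completion and 20% attrition with 83.3% and 16.7%, and show that the earlier work cited for attrition supports that rate.

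In either case, state that the test is two-sided and give section 1.5 the same attrition and power figures. The statement on 0.6 SD can stay.

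The cost is a text edit in two sections. Under the first option the stated power becomes slightly less favourable; under the second the attrition assumption becomes more optimistic and needs evidence. Holding a full 80% at 20% attrition would take 657 to 660 dyads, 27 to 30 more than planned. A gain of under 2 points does not require that.

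### The 80% power given for the EOWPVT-4 is that of one unadjusted two-sided 0.05 pairwise test; under the planned step-down minP procedure it is an upper limit, and how far power falls below it cannot be read from the plan

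*Combined protocol and SAP*

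**What the plan says.** Section 6.1, item 2, states "80% power to detect a 0.3 standard deviation (SD) difference in the primary endpoints language scores on the EOWPVT-4 and social-emotional skill scores". The social-emotional measure meant there is the DECA, and both scores are those taken at the 18-month visit. The same item names two contrasts, ROR + texts against ROR only and the three-component arm against ROR + texts, with about 20% attrition and "using 0.05 significance level". Section 1.5 says the sample will "achieve 80% power to detect a 0.3 standard deviation (SD) difference in language scores between" the same pairs of arms. Neither paragraph mentions multiplicity.

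Section 6.1, item 3, then sets the Aim 1 analysis. Step-down minP is applied "across outcomes and timepoints within each domain (language development, social-emotional development, and parenting"), and only secondary outcomes are tested "without adjustment for multiple comparisons". On the test statistic it says: "We will use ANOVAs to evaluate treatment effects on adjusted outcomes". Outcomes with a baseline and more than one follow-up become "individual- and baseline-adjusted outcomes from linear models with random individual-specific intercepts".

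The Data Points table (section 1.3 B) lists both the EOWPVT-4 (18 months only) and the CDI (enrollment, 9 and 18 months) as primary outcomes for language. The EOWPVT-4 therefore has no baseline. On covariates, the plan says: "For language outcomes, we will adjust for child age and sex in sensitivity analyses".

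**The concern.** The power paragraph and the analysis paragraph describe different tests. A step-down minP adjusted p-value is never smaller than the raw p-value, so adjustment can only lower the power of a given test. The EOWPVT-4 has no baseline score to recover precision, and age and sex stay out of its main analysis. Nothing stated for the main analysis offsets the loss.

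The trial was sized on the 80% figure. A reader of a null EOWPVT-4 result would take the chance of missing a true 0.3 SD effect to be one in five. Under some readings of the plan it is nearer one in three.

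**Working it through.** **Inputs.** From section 6.1: effect 0.3 SD, alpha 0.05, 630 enrolled, 175 per arm analysed. That section also expects 80% completion, and 0.8 × 630 = 504, or 168 per arm. Which number applies is a separate matter, so both are carried. Assumptions, because the plan gives no figures: equal correlation of 0 to 0.9 among the language test statistics, a range of CDI effects, and a test on the observed EOWPVT-4 score (the plan gives no adjustment rule for an outcome without a baseline).

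**1. Reproduce the 80%.** Two-sample t test with noncentrality δ√(n/2):
- n = 175: 0.3 × √87.5 = 2.806; two-sided 0.05 gives 79.9%.
- n = 168: 0.3 × √84 = 2.750; two-sided 0.05 gives 78.3%.
- At n = 175, one-sided 0.05 gives 87.6%, and Bonferroni for three tests gives 65.6%.

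Of these, only the unadjusted two-sided test gives the stated figure, so no multiplicity allowance is built in.

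**2. Three pairwise tests (EOWPVT-4 at 18 months, CDI at 9 and 18 months).** The largest |z| is compared with the critical value for the maximum of three, the next with that for two, and the last with 1.96. For independent tests the first critical value has tail area 1 − 0.95^(1/3) = 0.017, so z = 2.39. If the CDI does not move, EOWPVT-4 power is close to Φ(2.806 − 2.39) = Φ(0.42), about 66%. At correlation 0.9 the critical value is about 2.19, and Φ(2.806 − 2.19) = Φ(0.62), about 73%. Simulating the full step-down procedure (400,000 trials per cell) gives, over correlations 0 to 0.9:

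| Standardised CDI effect | 175 per arm | 168 per arm |
|---|---|---|
| 0 | 66-73% | 64-71% |
| 0.30 | about 75-76% | 73-75% |
| 0.40 | 79-80% | 77-78% |
| 0.45 or more | about 80% | about 78% |

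Power recovers as the CDI effect grows because a CDI test that rejects first relaxes the threshold left for the EOWPVT-4.

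**3. Baseline adjustment of the CDI.** With correlation r between all CDI visits, a raw effect of 0.3 SD becomes 0.3/√(1 − r²): 0.314, 0.346, 0.420 and 0.500 at r = 0.3, 0.5, 0.7 and 0.8. EOWPVT-4 power at 175 per arm is then about 75%, 77%, 79% and 80%.

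**4. Larger pairwise families, CDI not moving.** Five tests give 60-71% (175) or 57-68% (168). Nine tests, with all three arm contrasts included, give 56-61% or 53-59%.

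**5. minP on omnibus ANOVA p-values, then pairwise tests at 0.05.** Under arm means 0/0.3/0.6, power is about 80% (175) or 78% (168). If only one step has an effect, it is about 67-74% or 64-72%, taking CDI effects of 0 and 0.3 together.

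**The case against.** There are three serious replies.

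First, the plan never says that minP acts on pairwise p-values. Testing by ANOVA in a three-arm trial suggests an omnibus statistic at least as readily. On that reading, and with the plan's own additive pattern, the stated power survives. This stands, and it rules out any claim of a demonstrated shortfall.

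Second, section 6.1, item 2, names only the EOWPVT-4 and the DECA at 18 months as primary endpoints. If the CDI is secondary, it is tested unadjusted, the EOWPVT-4 is alone in its family and 80% stands. This fits the analysis text poorly. The minP domains there include parenting, which the power paragraph omits but the Data Points table lists as primary. A family spanning outcomes and timepoints would also have little meaning for one score at one visit. Still, the two sections conflict, so a family of three is the most natural reading rather than a stated fact.

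Third, a power near two thirds needs a CDI effect of zero. If the CDI also moves by 0.3 SD, the three-test loss at 175 per arm is roughly 0 to 5 percentage points, depending on correlation and baseline adjustment. This also stands. The planned confidence intervals for mean differences further limit the misreading of a null result.

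A reader might go on to infer that the DECA is underpowered too. The documents do not support that: the DECA has a baseline, and its planned adjustment can offset the multiplicity loss, to a degree set by a correlation the plan does not give. Nor does anything here show a Type I error problem.

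**Conclusion.** The stated power takes no account of the planned multiplicity procedure and is wrong as written. For an EOWPVT-4 pairwise contrast, 79.9% (175 per arm) or 78.3% (168) is an upper limit. The loss ranges from nothing to about 14 percentage points with three tests (79.9 − 66 at 175, 78.3 − 64 at 168), and more with larger families. Where it falls depends on the composition of the family, omnibus or pairwise statistics, the CDI effect, and the correlations, none of which the plan settles.

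A reader might infer that the trial has about 66% power for expressive vocabulary, or that it needs more participants. Neither follows. The 66% rests on pairwise minP, three tests, no CDI effect and low correlation, and no single replacement figure can be derived from the text. The point deserves correction because the change is specific and cheap, not because a shortfall has been shown.

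**What to change.** 1. In sections 1.5 and 6.1, item 2, label the 80% as the power of a single unadjusted two-sided 0.05 test, before the minP adjustment.
2. Reconcile the Data Points table with section 6.1, item 2, on which outcomes are primary. In section 6.1, item 3, state before unblinded outcome analysis which scores, timepoints and arm contrasts form each minP family, and whether its p-values are omnibus or pairwise.
3. Replace the figure with power simulated under that family and the analysed number per arm. State the assumed correlations and CDI effects, and refit the baseline adjustment in each resample so that the reference distribution matches the analysis.

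Do not insert an interim 66-80% sentence: it would commit the protocol to a family and an analysed number that are not confirmed.

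If the sponsor intends the EOWPVT-4 and DECA at 18 months to be the only primary endpoints, say so in the Data Points table and in section 6.1, item 3. Test them ahead of the other outcomes in their domains, and state how 0.05 is allocated across the arm contrasts.

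The cost is a few sentences and one simulation, with no change to sample size, visits or data. The downside is a less favourable stated power or, under the alternative, later testing of the CDI and the 9-month measures.
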